7.4.2 Efficacy analysis of secondary endpoints

The analysis will be based on the efficacy analysis set and the per protocol set.

- Paired numbers of VA (SVT and NSVT in separate), PVC, ICD or CRT-D shocks and ATP over 6 months of ACEI/ARB treatment and 6 months of ARNI treatment.
- Change in LVEF from date of treatment initiation over 6 months of ACEI/ARB treatment and 6 months of ARNI treatment.
- Change of NYHA level over 6 months of ACEI/ARB treatment and 6 months of ARNI treatment.
- Change proportion of NT-proBNP from date of treatment initiation over 6 months of ACEI/ARB treatment and 6 months of ARNI treatment.
- Number of hospitalizations for all causes and HF related hospitalizations during ACEI/ARB and ARNI treatments.
- Paired numbers of VA (SVT and NSVT in separate), PVC, ICD or CRT-D shocks and ATP over 3 months of ACEI/ARB treatment and 3 months of ARNI treatment.
- Number of hospitalizations for all causes and HF related hospitalizations during 3 months of ACEI/ARB and ARNI treatments.

Analysis of change from date of treatment initiation after 6 months of treatment (for paired quantitative endpoints)

Variables involved are number of SVT experienced, number of NSVT experienced, number of hourly PVC experienced, number of ICD or CRT-D shocks experienced, number of ATP experienced and time duration of NSVT experienced, as well as number of hospitalizations for

all causes and HF related hospitalizations.

The number of occurrences or duration of each variable within 3 months and 6 months and their changes from baseline will be descriptively analyzed by treatment group and compared between groups. The changes will be summarized by mean, standard error, median, quartiles, minimum and maximum. Because the baseline and post-treatment device data collection cycles are different, data will be standardized on a daily basis before the analysis of changes.

Normality will be checked for the values of each variable and changes calculated. If the data is parametric, paired t-tests will be performed; else if the data is non-parametric, Wilcoxon signed-rank test will be used.

Analysis of change from date of treatment initiation after 6 months of treatment (for continuous endpoints)

[figure not shown]
Variables involved are LVEF, NYHA and NT-proBNP.

The values of each variable at visits following 3 months and 6 months of treatment and their changes from baseline will be descriptively analyzed by treatment group and compared between groups. The changes will be summarized by mean, standard error, median, quartiles, minimum and maximum.

Normality will be checked for the values of each variable and changes calculated. If the data is parametric, paired t-tests will be performed; else if the data is non-parametric, Wilcoxon signed-rank test will be used.

NYHA is a qualitative variable, and NYHA level will be subject to Ridit transformation into a numerical Ridit value before the above analysis is carried out. The basic idea of Ridit transformation is to first determine a standard group (the sum of the frequencies of each treatment group of each grade is taken as the standard group), and then obtain the Ridit value R of each grade of the standard group. The weighted average of the frequency of each grade in each group and the R value of each grade in the standard group will be respectively used to obtain the average Ridit value of each group, and then compare between groups.

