5.1 Inclusion criteria

Participants eligible for inclusion in this study must meet all of the following criteria:

- 1. Male or female patients ≥ 18 and ≤ 80 years of age.
- 2. Implanted with an ICD or CRT-D within 2 weeks.
- 3. NYHA functional class II IV.
- 4. LVEF ≤40% (measured by echocardiography).
- 5. Signed informed consent must be obtained prior to participation in the study.

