Patients who discontinue from study should be scheduled for a final evaluation visit if they agree, as soon as possible, at which time all of the assessments listed for the final visit will be performed. At this final visit, all dispensed investigational product should be reconciled, and the adverse events and concomitant medications not previously reported must be recorded on

the eCRF. All treated patients should have a safety follow-up call conducted 30 days after last administration of study treatment.

Table 8-1 Assessment schedule

Period	Screening	A	CEI/ARB treatme	ent	ARNI treatment		
Visit name	1	2	3	4	5	6	7
Week/Month	0	1m (± 1w)	3m (± 2w)	6m (± 2w)	7m (± 1w)	9m (± 2w)	12m (± 2w)
Obtain informed consent	Х						
Inclusion/exclusion criteria	Х						
Demography	Х						
Date of birth							
Age							
Gender							
Race							
Height (cm)							
Weight (kg)							
BMI (kg/m²)							
Source of patient referral							
Patient HF History	Х						
Relevant medical history/current medical history	X						
Prior HF medications	Х						
Prior/Concomitant Medications	X	X	X	X	X	X	X
Implanted device	X						
Date of implantation							
ICD or CRT-D							
Primary prevention or secondary prevention							
Device data	Х	X	X	X		X	X
VA events (SVT, NSVT, PVC)							
ICD or CRT-D shocks (appropriate shocks and inappropriate shocks)							
Anti-tachycardia pacing (%)							

Physical examinations	Х	Х	Х	Х	Х	Х	Х
Electrocardiogram (ECG) data	Х		Х	Х		Х	Х
Holter monitor	Х			Х			Х
Echocardiographic data	Х			X			Х
LVEF (%)							
LVEDD (mm)							
Vital signs	X	Х	X	X	Х	X	X
Systolic blood pressure (mmHg)							
Diastolic blood pressure (mmHg)							
Heart rate average (bpm)							
Hematology test	X			X			X
Routine blood test							
Chemistry test							
Serum potassium (mEq/L)							
NT-proBNP (pg/mL)							
eGFR (mL/min/1.73m ²)							
blood pregnancy test							
Urinary pregnancy test	X			X			X
NYHA class (I-IV)	Х	Х	X	X	Х	Х	Х
Adverse Events	Х	Х	X	X	Х	Х	Х
Hospital admission data	Х	Х	X	X	Х	Х	Х
Study treatment administration	Х	Х	X	X	Х	X	Х
Study treatment dispense (ARNI)				Х	Х	Х	
Diary card collection		Х	Х	Х	Х	Х	Х
Study patient compliance assessment		Х	Х	Х	Х	Х	Х
Study completion status							Х

Abbreviations: ACEI = Angiotensin-converting enzyme inhibitor; ; ARB = Angiotensin receptor blockers; ARNI = Angiotensin receptor neprilysin inhibitor; ; CRT-D = cardiac resynchronization therapy-defibrillator;

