Baseline definition: Visit 1 data will be used as baseline of ACEI/ARB, and Visit 4 data as baseline of ARNI. If Visit 4 data are missing, the last available data before Visit 4 will be used.

Unless otherwise specified, the statistical description by visit only included the data of scheduled visits. For the evaluation involving maximum change, minimum change, abnormality, and clinically significant findings, the data of scheduled visits and unscheduled visits should be included.

Adverse events and medical history will be coded using MedDRA (see DMP for the specific version number).

Prior medications and concomitant medications will be coded using WHO Drug Dictionary (see DMP for the specific version number).

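### SAP 7.4.2 tests change from baseline for hospitalisation counts, but the two baselines are not comparable and the first may contain the device-implant admission

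*SAP*

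**What the plan says.** SAP 7.4.2 lists the endpoint as "Number of hospitalizations for all causes and HF related hospitalizations during ACEI/ARB and ARNI treatments". It then adds these counts, all-cause and HF-related alike, to the paired quantitative variables; the closing part of that list reads "time duration of NSVT experienced, as well as number of hospitalizations for", followed by the two kinds of admission. The rule for every variable on the list is "The number of occurrences or duration of each variable within 3 months and 6 months and their changes from baseline will be descriptively analyzed", and the two treatments are set against each other on these figures. Testing follows: "Normality will be checked for the values of each variable and changes calculated", then a paired t-test or a Wilcoxon signed-rank test. The same section says "Because the baseline and post-treatment device data collection cycles are different, data will be standardized on a daily basis before the analysis of changes".

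SAP 7.1 fixes the baselines: "Visit 1 data will be used as baseline of ACEI/ARB, and Visit 4 data as baseline of ARNI". Protocol 5.1 admits patients "Implanted with an ICD or CRT-D within 2 weeks". Protocol Table 8-1 has a row "Hospital admission data" marked at all seven visits, with no recall period for any of them.

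Two differences between sections matter here. Protocol 12.5.2 does not name hospitalisations among the variables analysed as changes; the SAP added them. Protocol 8.3.2 and SAP 4.1.2 describe arrhythmia- or HF-related admissions, while protocol 12.5.1 and SAP 7.4.2 describe all-cause and HF-related admissions.

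**The concern.** A change from baseline compares two treatments fairly only if the two baselines measure the same thing. Here they do not. The Visit 1 record is taken before study treatment, soon after a procedure that may itself have needed an admission. Nothing in either document keeps that admission out of the all-cause count. The Visit 4 record is made after six months on ACEI/ARB, so the ARNI change subtracts part of the comparator's own outcome.

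Take a patient with one implant admission recorded at Visit 1 and none afterwards. The ACEI/ARB change is 0 − 1 = −1 and the ARNI change is 0 − 0 = 0. ACEI/ARB is credited with preventing an admission that no drug affected.

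This is the only endpoint under the healthcare-utilisation objective. The SAP tests both the counts and their changes at 0.05 and does not say which is the main result, so a spurious change result could stand beside, and contradict, the valid comparison of counts.

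**Working it through.** **Number of pairs.** The plan gives no rate, SD, power or sample size for hospitalisations. Its only sample size is for SVT, and it is used here solely as the number of pairs. From 8/120 and 1/120 the discordant proportion is 0.0739 and the difference 0.0583. The exact two-sided McNemar (sign) test has power 0.7994 at 174 and 0.8024 at 175, so the plan's 175 is reproduced; 175/0.8 = 218.75, rounded up to 219.

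**Assumptions not in the documents.** Both drugs have the same admission rate r per day (0.3 to 1.0 per patient-year). Visit 1 looks back L days (14 to 365) and Visit 4 looks back W days (90 or 180). A share q of patients have the implant admission in the Visit 1 record. Each treatment period is 180 days. W = 90 is inferred from visits at Months 3 and 6.

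**Expected false difference (ARNI change minus ACEI/ARB change; positive is against ARNI).**

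- Per day: ACEI/ARB change = r − (r + q/L) = −q/L; ARNI change = r − r = 0. Difference = q/L, which does not depend on r or W.
- Not standardised: (180r − rW) − (180r − rL − q) = r(L − W) + q.

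**Rejection rates.** Wilcoxon signed-rank test, 175 pairs, gamma-Poisson counts, 300 simulated trials per scenario (Monte Carlo standard error at most √(0.25/300) = 2.9 percentage points).

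Standardised, r = 0.6 per patient-year, W = 90:

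| L (days) | q = 0.5: difference per 30 days | rejects | q = 0.25: difference per 30 days | rejects |
|---|---|---|---|---|
| 14 | 30 × 0.5/14 = 1.07 | 100% | 0.54 | 100% |
| 90 | 0.17 | 100% | 0.08 | 98% |
| 180 | 0.083 | 100% | 0.042 | 79% |
| 365 | 0.041 | 93% | 0.021 | 58% |

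Over r = 0.3 to 1.0 the ranges are 76% to 100% (q = 0.5) and 40% to 100% (q = 0.25). The low ends are at L = 365 and r = 1.0.

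Not standardised, W = 90, r = 0.6/365 = 0.00164 per day:

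| L (days) | q = 0: r(L − 90) | rejects | q = 0.5: r(L − 90) + 0.5 | rejects |
|---|---|---|---|---|
| 14 | −0.125 | 36% | +0.375 | 99% |
| 90 | 0.00 | 5% | +0.50 | 100% |
| 180 | +0.15 | 41% | +0.65 | 100% |
| 365 | +0.45 | 99% | +0.95 | 100% |

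At L = 14 the two components cancel when q = r(90 − 14) = 0.125, so the result can turn on recording practice alone.

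**Checks.**

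- With L = W = 180, q = 0 gives rejection of about 5%, but q = 0.5 still gives about 100%. The implant component does not depend on the inferred three-month window.
- With q = 0 and standardised data the mean difference is zero for any L and W. The Wilcoxon test still over-rejects, up to about 35% to 38%, when L = 14 and W = 90, because per-day counts from a short window are very skewed.
- Comparing the two six-month on-treatment counts, with no baseline subtracted, gives an expected difference of zero and rejection of about 2% to 7% in every scenario.

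**The case against.** The case for leaving the text alone has real content.

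- **Daily standardisation is a written instruction.** It sits in the paragraph covering the whole variable list; only its stated reason is confined to device data. If it covers admissions, unequal windows no longer shift the mean difference. This stands, but the implant component q/L remains and is largest for a short look-back.
- **The false difference is conditional.** A reader might infer that equal drugs must give a false result. The documents do not support that. They do not show how many implant admissions are entered at Visit 1, and the CRF and table shells that might settle it are not available. With none recorded and standardised data, or with equal windows, the mean difference is zero.
- **The Visit 4 record is not stated to be a three-month count.** A reader might take it as one from the visit schedule, but Table 8-1 gives no recall period. Likewise, the two-week limit in protocol 5.1 concerns time since implantation, not the Visit 1 look-back.
- **The direction without an implant admission is open.** A reader might expect the result to flatter ARNI in that case. It does so only if Visit 1 looks back less far than Visit 4 and the data are not standardised; with a longer look-back the sign reverses.
- **A valid comparison is already planned.** The counts themselves are tested in the same section and are unaffected. The implant problem is also clearest for the all-cause count, less so for HF-related admissions.

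**Conclusion.** The concern holds in a limited form. The SAP specifies, compares and tests a change from baseline for hospitalisations on two baselines that do not match, and neither document defines their look-backs or excludes the implant admission. This is a stated rule that can mislead, not just a missing detail.

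If the implant admission is recorded for a quarter to a half of patients, the false signal against ARNI is likely to reach significance even after daily standardisation. That conclusion rests on the assumed rates, shares, look-backs and count distribution; none comes from the documents. With no implant admission recorded, no direction can be claimed.

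It would go too far to say the healthcare-utilisation objective is lost: this is a secondary endpoint with a sound parallel analysis. The change should be made because the rule adds nothing valid and can produce a false finding.

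**What to change.** In SAP 7.4.2, remove all-cause and HF hospitalisations from the change-from-baseline analysis, in line with protocol 12.5.2. Compare only:

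- admissions starting from the first ACEI/ARB dose to before the first ARNI dose, with
- admissions starting from the first ARNI dose to Month 12 or withdrawal,

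each divided by the days of observation in that period. State that the implant admission is not counted.

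The per-day basis is needed because the SAP's efficacy analysis set includes patients who withdrew early after a single ARNI dose. With raw counts, their shorter ARNI follow-up would yield fewer ARNI admissions and could favour ARNI.

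The cost is a short SAP edit and one table column dropped. No data change, assuming admission start dates are held in the hospital admission record, whose contents the documents do not itemise.

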4.4 Past and concomitant medication and concurrent treatment

The CRF collects the drug name, total daily dose and unit, frequency of administration, route of administration, start date, end date, ongoing or not, and indication for prior and concomitant medications.

The CRF collects the name, start date, end date, ongoing or not, and indication of concomitant treatments (non-drug concomitant treatments, including surgery).

4.5 **Protocol Deviation and Medication Compliance**

Protocol deviations will be recorded by the clinical monitor.

Medication compliance for ACEI/ARB and ARNI is defined as: total actual dose/total planned dose *100%. Overall medication compliance for ACEI/ARB and ARNI will be summarized.

5. Statistical Hypotheses

For details, see section 7.4 Efficacy Analysis.

6. Analysis Datasets

The analysis data sets of this study are as follows.

Screened set

It includes all subjects who have signed the informed consent form.

Safety Analysis Set, SS

It includes all subjects who had received at least one dose of study treatment. Analyses will be performed according to the study treatment received. The safety analysis set will be used for all analyses except the efficacy analysis.

Efficacy Analysis Set

It includes SS subjects who have received ARNI at least once and completed 12 months of complete treatment and follow-up or who have early withdrawn from the study after receiving ARNI at least once. The efficacy analysis set will be used as the primary population to analyze the efficacy variables.

Per Protocol Set, PPS

It includes subjects in efficacy analysis set who had no major protocol violations, and the PP population will be used for efficacy analysis.

7. Statistical Methods

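### Per-day standardisation is stated only for changes from baseline: the period counts compared between treatments are not adjusted for days observed, and the two changes rest on very unequal baselines

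*SAP*

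**What the plan says.** SAP 7.4.2 lists paired numbers of SVT, NSVT, PVC, shocks and ATP, and hospitalisations, over 6 months and over 3 months of each treatment. NSVT duration is analysed with them. Two quantities are described and compared between treatments: "The number of occurrences or duration of each variable within 3 months and 6 months and their changes from baseline". Testing covers both: "Normality will be checked for the values of each variable and changes calculated", followed by a paired t-test or a Wilcoxon signed-rank test.

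The only rule on observation time, with its reason, is: "Because the baseline and post-treatment device data collection cycles are different, data will be standardized on a daily basis before the analysis of changes". One variable is a rate by definition: "number of hourly PVC experienced". Protocol 12.5.2 contains no standardisation.

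On baselines, SAP 7.1 says "Visit 1 data will be used as baseline of ACEI/ARB, and Visit 4 data as baseline of ARNI". Inclusion criterion 2 (Protocol 5.1) reads "Implanted with an ICD or CRT-D within 2 weeks". Neither document states how many days of device data make up either baseline.

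On who is analysed, the efficacy analysis set (SAP Section 6) takes patients who completed 12 months "or who have early withdrawn from the study after receiving ARNI at least once". SAP 7.2.1 imputes no missing data apart from certain dates.

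**The concern.** A count needs a denominator when periods differ in length. Every patient in the efficacy set has reached ARNI, so early withdrawal within that set falls in the second period. A patient who leaves at Month 9, with events counted only to that visit, has fewer ARNI events by construction. The SAP does not say whether such a count enters the paired test as it stands, is scaled, or is dropped. If it enters as it stands, the error favours ARNI.

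The standardised analysis does not make up for this. Visit 1 can hold only the days since implantation, while Visit 4 follows six months on ACEI/ARB. Comparing the ARNI change with the ACEI/ARB change therefore sets a change from a long on-comparator baseline against a change from a very short baseline after implantation. The result depends partly on the early post-implant rate, which says nothing about either drug.

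**Working it through.** **The plan's own figure.** SAP 3.2.2 assumes a mean paired difference of −3, SD 10, and states more than 95% power. With two-sided alpha 0.05 and n = 175: 3/10 × √175 = 3.97, and Φ(3.97 − 1.96) = 0.978 (noncentral t: 0.9765). At n = 219 the power is 0.993. The stated figure reproduces. Per-day scaling leaves it unchanged when both periods are complete and equal.

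**Visit windows.** Protocol Table 8-1 allows ±2 weeks at Months 6 and 12. With 6 months = 182.6 days:
- ACEI/ARB period: 182.6 ± 14 = 169 to 197 days.
- ARNI period: 182.6 ± 28 = 155 to 211 days.
- Within-patient ratio ARNI:ACEI/ARB: 154.6/196.6 = 0.79 to 210.6/168.6 = 1.25.

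Either period can be the longer one, so the windows add noise without a direction.

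**Early withdrawal.** If a share q of analysed patients is observed for only a fraction f of the ARNI period, and partial counts are used, the mean ARNI count falls by q × (1 − f). With q = 10% and f = 0.5 this is 5%.

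A simulation shows what that does to the paired t-test. Assumptions: n = 175, gamma-Poisson counts, no treatment effect, mean 5 (gamma shape 0.5) or mean 10 (shape 1) events per 6 months, exit spread evenly over the ARNI period, 3,000 trials per case.

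| Share leaving during ARNI | Mean spurious difference, events per patient | Raw counts: rejections | Per-day rates: rejections |
|---|---|---|---|
| 0% | 0.0 | 4.6–5.2% | 4.6–5.2% |
| 5% | −0.12 to −0.24 | 7.2–10.0% | 5.3–5.4% |
| 10% | −0.24 to −0.49 | 15.2–23.3% | 4.4–4.5% |
| 20% | −0.49 to −0.98 | 41.5–65.4% | 4.5–4.6% |

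The planned difference is −3. The documents give neither the share leaving during ARNI nor count means, so the table is a range under assumptions. The signed-rank alternative was not simulated.

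**Change versus change.** Let R0, R1 and R2 be daily rates at Visit 1, on ACEI/ARB and on ARNI. If Visit 4 stands for the whole ACEI/ARB period, the compared quantity is

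(R2 − R1) − (R1 − R0) = R2 − 2R1 + R0.

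Its expectation is the ARNI minus ACEI/ARB difference plus (post-implant rate − ACEI/ARB rate). A high early rate makes ARNI look worse, and a low one makes it look better.

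Variance under Poisson counts with a common rate, 182-day periods and a 14-day baseline:
- Change versus change: 1/182 + 4/182 + 1/14 = 18/182.
- Direct difference R2 − R1: 2/182.
- Ratio: 9.0, so 3 times the SD.

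If Visit 4 means Months 3–6 only, write Ra and Rb for the two ACEI/ARB halves, so R1 = (Ra + Rb)/2. The contrast is R2 − 1.5Rb − 0.5Ra + R0, with variance (1 + 4.5 + 0.5 + 13)/182 = 19/182 and ratio 9.5.

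If variation that does not shrink with period length dominates, the ratio tends to (1 + 4 + 1)/2 = 3. A baseline shorter than 14 days raises the Poisson ratio. One event in a 14-day baseline scales to 182.6/14 = 13 per 6 months.

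**The case against.** Several stronger readings are tempting, and the documents do not support them.

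- A reader might infer that every patient who stops ARNI has a shortened count. Protocol 9.1.1 keeps patients who discontinue treatment in the study and asks them to return for scheduled assessments where possible, and the implanted device can still be read. Protocol 2.1 ignores treatment discontinuation, though only for the primary estimand. What shortens the ARNI period is loss of device follow-up.
- A reader might infer that the analysis will favour ARNI as a matter of fact. The SAP does not say whether a truncated count is used or treated as missing. Protocol Section 8 offers a final visit with the final-visit assessments, so partial counts can exist, but their use is not specified.
- A reader might treat the visit windows as part of the bias, or both baselines as 2 weeks long. The windows have no direction. The short baseline belongs to ACEI/ARB alone.
- A reader might call the change comparison no treatment effect at all. If the early post-implant rate equals the ACEI/ARB rate, and the latter is stable over the period, its expectation is the treatment difference. It is then imprecise, but not wrong.

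It can also be said that the standardisation sentence was meant for all count data. Its wording and its reason, the different baseline cycle, are both tied to changes, and hospitalisations have no device cycle. If wider use is intended, one sentence would settle it. Finally, Protocol 12.5.2 prespecifies change from treatment initiation for these variables, so deleting that analysis would depart from the protocol.

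These points limit the size and certainty of the effect. They do not supply a denominator for the period counts.

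**Conclusion.** The point stands for secondary endpoints and should be fixed. As written, period counts of SVT, NSVT, shocks, ATP and hospitalisations, and NSVT duration, are compared between treatments with no adjustment for days observed. PVC is exempt because it is hourly. Any truncation from early withdrawal in the efficacy set falls on the ARNI side, and unscaled partial counts would favour ARNI.

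The size is conditional. The 5% fall assumes that 10% of analysed patients lose follow-up halfway and that their partial counts are used. The inflated rejection rates rest on the assumed exit shares and count distributions. With complete, equal follow-up there is no bias.

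The change-versus-change comparison is a poor basis for judging ARNI against ACEI/ARB. Its variance is about 9 times that of the direct rate difference under Poisson counts and a full 14-day baseline (nearer 3 if other within-patient variation dominates), and its expectation moves with the post-implant rate.

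**What to change.** In SAP 7.4.2:

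1. Make the paired difference in events per day of device follow-up, ARNI period minus ACEI/ARB period, the main analysis of the device counts, for both the 3-month and 6-month comparisons. Use days in study as the denominator for hospitalisations, treat NSVT duration in the same per-day way, and leave PVC hourly.
2. State how a truncated period enters the analysis, and how days of device follow-up are counted.
3. Define the Visit 1 and Visit 4 device windows in days, including whether Visit 4 covers the whole ACEI/ARB period or only the time since Month 3.
4. Keep the change-from-baseline comparison for counts as secondary or descriptive, and align Protocol 12.5.2 with this.

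The cost is small wording changes in the SAP and protocol and some programming. No new data are needed, and the stated power is unaffected when follow-up is complete and equal.
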